## **STATISTICAL ANALYSIS PLAN**

**Title:** Brief Electronic Intervention for Heavy Drinking and Sex Risk Among Men who have sex with Men  
Seeking HIV Testing

**NCT#:** NCT03435783

**Date of document:** Last reviewed and approved by Brown IRB on 7/21/17

**Statistical analysis plan.** We hypothesized that participants using the web-based intervention would report (1) fewer new anal sex partners, (2) fewer condomless anal sex events, and (3) lower frequency of drinking, (4) lower frequency of binge drinking, and (5) a lower average number of drinks per drinking day versus the control group. These hypotheses will be evaluated using an intention-to-treat comparison of the rates of our primary outcomes at 1-, 2-, and 3-month follow-ups, using incidence rate ratios (IRRs) and 95% CI. Given the count nature of much of the data, we will use a Poisson regression covarying for key baseline covariates, and compare IRRs across the two treatment conditions at each time point. As conclusions about statistical significance will be limited due to the small sample, clinically meaningful differences in the pattern of IRRs and means (for alcohol use variables) across groups will be used to evaluate our hypotheses. However, if available data produce stable results, generalized estimating equations (GEEs) using binomial distributions and logit-link functions will also be used to explore differences in these outcomes across time and treatment condition. We will also explore the potential influence of the intervention on secondary outcomes and exploratory mediators. IRRs and descriptive data will be used to compare the groups in terms of their frequency of talking to partners about their status, whether they sought additional HIV testing, STI screening or information about PrEP. Descriptive mean comparisons and linear regressions controlling for baseline values will be used to compare whether HIV knowledge and perceived risk, peer safe sex norms, and safe sex behavioral skills differ across the groups.

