Phase 1c: Theatre testing of BI alpha-version. We will recruit a sample of 10 MSM, using the eligibility criteria from Phase 1b, to conduct a “theatre test” of the BI. MSM who participated in earlier phases will be excluded to provide different perspectives. Participants who are seeking HIV testing at the target venues will be recruited using a screening item concerning their interest in the study that will be included on the standard post-test assessment, and their participation will be anonymous. Interested participants will simply wait in the testing room for study staff after VCT is complete. Staff will then provide them with a tablet and headphones in order to complete the full intervention. Afterward, participants will complete a brief questionnaire and interview about their perceptions of the acceptability and feasibility of delivering a BI in this environment, as well as comments they have about each BI component. Participants will receive \$30 for completing the theatre test.

Qualitative analysis. Recordings of all focus groups and interviews will be transcribed via commercially available software. Data will be analyzed using modified grounded theory methods⁹⁰, with two independent coders arriving at a consensus on major themes identified. This qualitative data will allow us to refine the assessment instruments and BI components for population sensitivity. As such, the study team will review the analysis, and assess the strengths/weaknesses of each of the components based on these findings.

C.4.2. PHASE 2: PILOT TESTING

Specific Aim 2 is to conduct a pilot randomized controlled trial of our BI, and explore preliminary evidence of its efficacy for reducing sexual risk and alcohol use among a sample of high-risk MSM seeking HIV testing in community venues. As such, we will randomize 40 MSM who receive HIV testing at the identified venues to either the standard VCT group + attention-matched control (AC), or the VCT + Intervention (BI) group. We will test the hypothesis that those in the BI group will report reductions in sex risk outcomes, sex under the influence of alcohol, and alcohol use at 1-, 3-, and 6-month follow-ups compared to the VCT+AC group.

C.4.2.1. Methods

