Baseline/Eligibility Assessments. The SDS¹⁷ will be used to assess symptoms of substance dependence for methamphetamine, cocaine, heroin/opiates, and alcohol. The SDS has demonstrated good validity and excellent reliability with respect to these drugs ($\alpha=0.80-0.85$)^{14; 15; 17}. In addition, a 30-day Timeline Follow Back (TLFB)^{18; 19}, administered online, will be used to assess alcohol use and sexual behavior during that period. The TLFB presents a calendar of each recall period, and participants respond by clicking on a box that represents a given day, answering several questions about that day. Questions will assess the number of standard drinks consumed on that day, the number of hours over which these drinks were consumed, the total number of sex partners, their relationship with each (e.g., steady vs. casual), the HIV status of each (e.g., HIV+, HIV-, or unknown), whether they asked about their partner’s HIV/STI status or the last time they were tested, sex acts performed with each, condom use for each act, and whether sexual activity took place while under the influence of alcohol. Meta-analyses have shown that TLFBs for assessing alcohol use and sex behavior are reliable when administered electronically and online²⁰. Other studies explicitly comparing online vs. in-person TLFBs for sexual behavior²¹, and comparing the TLFB to biological measures for alcohol use²² have confirmed the validity of online TLFBs. TLFB data will be used to determine participants’ drinking eligibility, while single items will assess all other eligibility criteria. Finally, stages of change will be assessed using the Stages of Change (Short Form)²³ and a 4-item stages of change measure for HIV-risk²⁴⁻²⁶.

Efficacy outcomes. Our primary outcomes will be the number of unprotected anal sex events, number of sex events under the influence of alcohol, frequency of drinking, and the

number of heavy drinking days over the past month. Outcomes will be assessed via 30-day Timeline Follow Back (TLFB)^{91, 93} at each follow-up.

Secondary outcomes. We will also assess whether participants talked to their partners about their HIV/STI status and recent testing, and whether during each follow-up window, participants engaged in self-initiated HIV testing, sought STI screening, or sought information about pre-exposure prophylaxis. Change motivation and stages will also be explored as secondary outcomes.

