Primary analyses. Our hypotheses related to Specific Aim 2 are that participants in the intervention group will report (1) fewer unprotected anal sex events, (2) fewer events involving sex while under the influence of alcohol, and (3) lower frequency of drinking and a reduced number of heavy drinking days versus the control group. These hypotheses will be evaluated using an intention-to-treat comparison of the rates of our primary outcomes at 1-, 3-, and 6-month follow-ups, using an incidence rate ratio (IRR) and 95% CI. Given the count nature of the data, we will use a Poisson regression covarying for key baseline covariates, and compare IRRs across the two treatment conditions at each time point. As conclusions about statistical significance will be limited due to the small sample, clinically meaningful differences in the pattern of IRRs and means (for alcohol use variables) across groups will be used to evaluate our hypotheses. However, if available data produce stable results, generalized estimating equations (GEEs) using binomial distributions and logit-link functions will also be used to explore differences in these outcomes across time and treatment condition. We will also explore the potential influence of the intervention on secondary outcomes and exploratory mediators. IRRs and descriptive data will be used to compare the groups in terms of their frequency of talking to partners about their status, whether they sought additional HIV testing, STI screening or information about PrEP. Descriptive mean comparisons and linear regressions controlling for baseline values will be used to compare whether HIV knowledge and perceived risk, peer safe sex norms, and safe sex behavioral skills differ across the groups.

C.4.3. Recruitment

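### The protocol and the SAP, approved on the same date, name different primary outcomes: alcohol-involved sex is dropped and two outcomes are added without explanation

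*SAP*

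**What the plan says.** **Protocol.** Section C.4.2.2 Measures, under Efficacy outcomes, states: "Our primary outcomes will be the number of unprotected anal sex events, number of sex events under the influence of alcohol, frequency of drinking". The same sentence ends with a fourth outcome, the "number of heavy drinking days over the past month". The Data Analysis Plan turns these into hypotheses, the second of which reads "2) fewer events involving sex while under the influence of alcohol". The third covers "lower frequency of drinking and a reduced number of heavy drinking days versus the control group". Section C.4.2 (Phase 2: Pilot Testing) states the overall Phase 2 hypothesis in the same sense: "those in the BI group will report reductions in sex risk outcomes, sex under the influence of alcohol, and alcohol use".

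**SAP.** Its single paragraph hypothesises that users of the intervention "would report (1) fewer new anal sex partners, (2) fewer condomless anal sex events, and (3) lower frequency of drinking", then adds less frequent binge drinking and fewer drinks per drinking day. It has no separate list of primary outcomes. All five are primary because the next sentence evaluates these hypotheses on the rates of the primary outcomes. Its secondary outcomes are talking with partners about status, HIV testing, STI screening and seeking PrEP information. Its mediators are HIV knowledge and perceived risk, peer norms and safe-sex skills.

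Both documents carry an IRB approval date of 7/21/17.

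**The concern.** Sex while drinking is the only protocol primary outcome that records the two target behaviours together. The protocol's description of the combined intervention (C.4.1) says it addresses how alcohol use and HIV-risk behaviour relate. A reader following the SAP would find no outcome of that kind at any level, and would find two outcomes treated as primary that the protocol never lists.

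The trial randomises 40 men. Both texts accept that significance testing will be of limited use and say the hypotheses will be judged by clinically meaningful differences in the rate ratios and means. Neither gives a threshold or a multiplicity rule. When the reading rests on a pattern, a list of outcomes fixed in advance is the main protection against choosing the favourable ones. Two lists in force at once weaken that protection.

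One of the added outcomes also lacks a described source. The Timeline Follow-Back (TLFB) is said to record "the total number of sex partners, their relationship with each (e.g., steady vs. casual", among other items, but the description does not say how a new partner is told apart from an earlier one.

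**Working it through.** The documents give no figure to reproduce, so the check sets the two lists side by side.

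| Outcome | Protocol (C.4.2.2, Efficacy outcomes) | SAP |
|---|---|---|
| Anal sex events without a condom | primary | primary |
| Drinking frequency | primary | primary |
| Heavy or binge drinking | primary | primary |
| Sex events under the influence of alcohol | primary, and a named hypothesis | absent at every level |
| New anal sex partners | not listed at any level | treated as primary |
| Mean drinks per drinking day | not listed at any level | treated as primary |

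**Outcome count.** Matched 3, dropped 1, added 2. From the protocol's four: 4 − 1 + 2 = 5, which is the SAP's number.

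**Comparisons.** Each document has three follow-ups, with a between-arm comparison at each.
- Protocol: 4 × 3 = 12, of which 1 × 3 = 3 have no counterpart in the SAP.
- SAP: 5 × 3 = 15, of which 2 × 3 = 6 concern outcomes that the protocol does not list.
- Check: 12 − 3 + 6 = 15.

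The follow-up months also differ (1, 3 and 6 in the protocol; 1, 2 and 3 in the SAP). That is a separate discrepancy and does not alter these counts.

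**Matching assumption.** The table treats unprotected and condomless events as the same outcome, and heavy drinking days and binge frequency as the same outcome. The SAP does not define binge drinking. If it means something other than the protocol's heavy drinking days, the tally becomes 2 matched, 2 dropped and 3 added (4 − 2 + 3 = 5), a wider gap.

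**Data already collected.** According to the Baseline/Eligibility Assessments text, the TLFB asks each day for the number of standard drinks and whether sex took place under the influence of alcohol. The dropped outcome and drinks per drinking day can therefore both be computed. For new partners, the text gives partner numbers and a relationship category with one illustrative example, and describes no first-time item.

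**The case against.** The best defence is that the additions are not foreign to the trial. Specific Aim 2 describes the primary outcomes broadly as sexual risk behaviour and alcohol use, and both additions fall in those domains. Drinks per drinking day follows from the daily drink counts, and the protocol's analysis plan already expects to compare means for alcohol variables. This is also a small pilot that does not claim confirmatory inference. All of that stands, but it does not settle the conflict: the protocol goes on to name four specific outcomes, and the SAP's list differs from it without comment.

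A second defence is that no text says which list was intended, so a remedy that favours the protocol picks a winner. That is fair. The protocol list is a reasonable default because alcohol-involved sex appears in its design, measures and analysis sections and has a described data source. A documented change should be able to override that default.

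A reader might also infer four stronger points, which the documents do not support:

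- *That the alcohol-involved sex hypothesis has no planned analysis.* The protocol's Data Analysis Plan gives it an intention-to-treat Poisson comparison with a rate ratio and 95% CI at each follow-up. The protocol file is itself headed as a statistical analysis plan. The defect is an unresolved conflict between two plans, and the documents contain no results to show which was followed.
- *That dropping the outcome removes the test of the alcohol–sex link.* The count can fall because drinking falls or because sex falls. It captures joint behaviour and does not test the link.
- *That the case for a combined over an alcohol-only intervention goes untested because of the omission.* The comparator is an attention control of diet and exercise videos. No outcome list could make that contrast here.
- *That new partners cannot be derived.* The relationship categories are given only as an example, the study measures in Appendix E are not reproduced, and the SAP does not say the count comes from the TLFB. The supportable statement is that the documents do not say how a new partner is identified.

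**Conclusion.** The concern holds as a contradiction between two texts with the same date. Of the protocol's four primary outcomes, one has no place in the SAP; of the SAP's five, two have no place in the protocol. That is 3 of 12 and 6 of 15 outcome-by-visit comparisons. These counts measure the mismatch; they do not estimate bias.

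Under the SAP, drinking and sexual risk are each still compared between arms, but no outcome captures their occurring together. The conflict decides which results count as the trial's answer, so it needs correction even in a pilot. The conclusion rests on the matching of outcome names set out above and on the SAP sentence that gives its hypotheses primary status. The mismatch itself is certain from the text; whether new partners can be measured is open.

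**What to change.** 1. Reconcile the two lists into one primary list that appears identically in both documents, and state which document governs.
2. Restore the number of sex events under the influence of alcohol to the SAP, with the same Poisson rate-ratio comparison as condomless anal sex events. The item is already collected, so this costs only wording.
3. Label new anal sex partners and mean drinks per drinking day as secondary, unless the change is dated and justified as made before outcome data were seen. This also costs only wording.
4. Confirm that the study measures identify a first-time partner, and say in the SAP how the count is formed. If they do not, add the item if data collection still allows it, at the price of a slightly longer TLFB and IRB approval of the changed measure. Otherwise remove that hypothesis.

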Eligibility. Criteria for inclusion in this portion of the study are: (1) Male, (2) age 18 or older, (3) fluent in English, (4) self-reported unprotected anal sex with a casual male partner at least once in the past 3 months¹², (5) heavy alcohol use during the past 2-weeks (>14 drinks per week, or at least one occasion of 5+ drinks)¹³, (6) register a breath alcohol content of .000 upon recruitment, (7) no history of complex alcohol withdrawal, (8) scoring < 4 on severity of dependence scale (SDS) for methamphetamine¹⁴, and < 3 on the SDS for cocaine and heroin/opiates^{15; 16}, (9) HIV-negative as indicated during their preliminary HIV testing, and (10) willing to provide phone and email contact information (see Design Considerations section below for further detail). Participants who test HIV+, score highly on the SDS, or participated in Phase 1 of the research will be excluded from participation. Those testing HIV+ will be referred to a comprehensive care clinic at the Miriam Hospital for treatment, as per the standard protocol of our collaborating agency. Those with high SDS scores will be provided with lists of local MSM-friendly drug treatment providers.

Recruitment. We will recruit participants from among those seeking HIV testing at the identified community-based venues. Patrons who are interested in participating indicate this on

their standard HIV testing “exit” form, which is anonymous. After APRI staff deliver negative results, participants will remain in a private room, where our research study staff will enter and provide further information about the study.

Baseline Assessment. All assessments will be completed on the tablet and administered by a research assistant that is blind to experimental condition. Study staff will first acquire informed consent and deliver the tablet to begin collecting baseline/screening measures. While ineligible participants will be informed of this on the assessment screen, eligible participants will then proceed directly to complete other baseline measures. Participants will receive \$50 for the baseline session, which may take up to 90 minutes.

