Exploratory Mediators. As exploratory measures, we will include brief measures of possible mediators of the intervention effect, based on mediators identified in the original BIs. These will include HIV-related knowledge, perceived risk for HIV, peer safe sex norms, and safe sex behavioral skills (e.g., condom negotiation, partner communication skills, self-efficacy)²⁷⁻²⁹.

General participant characteristics. Participants will also provide information about general demographic characteristics (e.g., age, ethnicity, income, educational level); general health; current relationship status and relationship history; self-reported history of other sexually transmitted infections (chlamydia, genital warts, gonorrhea, herpes, syphilis, trichomoniasis, Hepatitis B, Hepatitis C); drug use behaviors (SDS), and utilization of other health and social services. We will also administer the Client Satisfaction Questionnaire, a brief 8-item measure assessing satisfaction with services⁹⁵.

C.4.2.2. Data Analysis Plan

Descriptive/Exploratory analyses. Behavioral data (e.g., alcohol use and sex risk behaviors) will be tabulated using contingency tables within each condition at baseline and for each follow-up period. We will examine study retention rates at each follow-up and generate a CONSORT flow-diagram.

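### Does drinks per drinking day (SAP hypothesis 5) need a stated rule for men who report no drinking day?

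*SAP*

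**What the plan says.** The SAP lists five hypotheses. The third and fourth concern how often men drink and how often they binge; the fifth predicts "a lower average number of drinks per drinking day versus the control group". All five fall under one sentence: "These hypotheses will be evaluated using an intention-to-treat comparison of the rates of our primary outcomes". The model is Poisson regression with incidence rate ratios (IRRs) at each visit. Because the sample is small, the SAP says that "clinically meaningful differences in the pattern of IRRs and means (for alcohol use variables) across groups will be used to evaluate our hypotheses".

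The protocol does not list drinks per drinking day. Its Efficacy outcomes paragraph (C.4.2.2 Measures) reads "Our primary outcomes will be the number of unprotected anal sex events, number of sex events under the influence of alcohol, frequency of drinking" and then adds the count of heavy drinking days. Both alcohol outcomes take the value zero without difficulty. The same paragraph gives the window: "Outcomes will be assessed via 30-day Timeline Follow Back". The SAP states no window.

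Protocol C.4.2.1 (Eligibility) requires "heavy alcohol use during the past 2-weeks (>14 drinks per week, or at least one occasion of 5+ drinks". Under Descriptive/Exploratory analyses, the protocol says behavioural data "will be tabulated using contingency tables within each condition at baseline and for each follow-up period".

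**The concern.** For a man with no drinking day in the window the ratio is 0/0. The Poisson model does not rescue it, since an offset of log(drinking days) is also undefined at zero.

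Every eligible man has a value at baseline, so the value can be lost only after randomisation. Hypothesis 3 expects the intervention to lower drinking frequency, which is what produces such men. Dropping them would remove randomised men on account of something the intervention is meant to change, under a sentence that promises intention-to-treat. Coding them as zero keeps them, but then the measure mixes abstinence with quantity per occasion.

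The SAP reads patterns of IRRs and means and does not rely on significance tests. The point estimate is therefore what will be interpreted, and it depends on a rule nobody has written down.

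**Working it through.** The documents give no figure to reproduce here: no abstinence rate, mean, SD, power or dropout. The number randomised is 40 (protocol C.4.2); 20 per arm is assumed because no ratio is stated. The remaining inputs are also assumptions.

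**1. Effect of the rule when the men who stop are typical drinkers.** With *k* zero-day men in an arm of 20, the zero-coded mean is (20 − *k*)/20 of the drinkers' mean.
- *k* = 1: 19/20 = 0.95.
- *k* = 2: 18/20 = 0.90.
- The drinkers-only ratio stays at 1.00.

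**2. Effect when they are not typical.** Suppose each arm would have 10 men at 3 and 10 men at 7 drinks per drinking day (mean 5.00), and nobody who continues changes quantity.

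| Who stops in the intervention arm | Drinkers-only mean (ratio) | Zero-coded mean (ratio) |
|---|---|---|
| 2 lighter men | (8×3 + 10×7)/18 = 5.22 (1.04) | 94/20 = 4.70 (0.94) |
| 2 heavier men | (10×3 + 8×7)/18 = 4.78 (0.96) | 86/20 = 4.30 (0.86) |
| 4 lighter men | (6×3 + 10×7)/16 = 5.50 (1.10) | 88/20 = 4.40 (0.88) |

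The drinkers-only figure can fall on either side of 1, so the direction of any distortion is unknown.

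**3. How many men are likely to be affected.** A man who drinks on one day in seven has no drinking day with probability (6/7)^14 = 11.6% over 14 days and (6/7)^30 = 1.0% over 30 days. The chance of at least one zero-day man among 40 is 1 − (1 − *a*)^40: 33% at *a* = 1%, 55% at 2%, 87% at 5%.

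A simulation applied the entry rule to a 14-day baseline, with a 30-day follow-up window and 4,000 trials per setting. Daily drinking probability was uniform from 1/14 to 0.3 or to 0.6. Quantity had mean 5 and log-SD 0.4, and its correlation with frequency was −0.4, 0 or 0.4.

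| Intervention effect | Zero-day men, intervention arm | Median ratio, drinkers-only | Median ratio, zero-coded |
|---|---|---|---|
| None | 0.05–0.26 (per arm) | – | – |
| Frequency down 25% | 0.13–0.65 | 0.99–1.01 | 0.98–1.00 |
| Frequency halved | 0.42–1.68 | 0.99–1.00 | 0.92–0.98 |
| 10% stop, others unchanged | 2.0–2.2 | 1.00 | 0.90 |

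The men who stop in the last row were drawn at random, so the table shows the size of the gap and says nothing about direction. Step 2 covers direction.

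**4. Comparison with sampling error.** At log-SD 0.4 the coefficient of variation is √(exp(0.16) − 1) = 0.417. The standard error of the log ratio is 0.417 × √(2/20) = 0.132, and exp(1.96 × 0.132) = 1.29. A true ratio of 1 is therefore compatible with estimates from about 1/1.29 = 0.77 to 1.29. Every ratio in steps 1 to 3 lies inside that range.

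**The case for a change.** The best case for acting is that it costs a sentence or two. The daily drink counts are already collected, and fixing the rule before analysis removes a choice that could otherwise be made after seeing the data. The two codings are applied to the same men, so the gap between them is systematic and not chance. Step 2 shows that the rule alone can put the estimate on opposite sides of 1, in a plan that reads point estimates.

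Most of this stands as fact: the rule is unstated, a drinkers-only summary is not intention-to-treat, and the direction cannot be predicted. What does not follow is that the plan has to change.
- Either coding, once chosen, would close the gap. That makes it a request for a definition and not the correction of an error. The SAP nowhere says such men will be dropped.
- A gap of about 0.10 needs around two of 20 men to stop completely. The documents supply no such rate. With frequency cut by a quarter, the two codings differ by about 0.02 or less.
- Systematic or not, a shift of 0.10 within limits of 0.77 to 1.29 gives no reader grounds for a different conclusion from 40 men.

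**Conclusion.** No change follows. This is an ordinary gap in a one-paragraph SAP that defines none of its outcomes operationally, and analysts have sensible ways to fill it. Frequency is hypothesis 3, so hypothesis 5 reads naturally as quantity on the days when a man drinks, reported with the number of men behind the mean. The protocol's 30-day Timeline Follow-Back supplies the window. The tabulation by condition and visit that the protocol already plans would ordinarily show men with no drinking.

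The consequence is confined to one hypothesis of five. Hypotheses 3 and 4 are defined at zero and still credit a man who stops drinking, so a benefit through abstinence is not lost from the pattern the SAP intends to read. On the assumptions above, well under one man per arm is affected if the intervention does nothing, and about two per arm if a tenth of the intervention arm stops. The resulting gap of about 0.10 is smaller than the sampling uncertainty.

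These sizes rest on 20 men per arm, the assumed drinking distributions and a 30-day window. A much higher abstinence rate would widen the gap: with four of 20 lighter drinkers stopping, the ratios are 1.10 and 0.88. Even these lie within the sampling limits for a pilot of this size. A drinkers-only result should simply be read as such, with no presumption about which way it leans.

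### SAP hypothesis 5 is a per-man average, yet the only model given for its IRR and 95% CI is Poisson regression, with no offset and no robust or scaled variance

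*SAP*

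**What the plan says.** All of this is in the single paragraph of the SAP.

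- **Outcome.** Hypothesis 5 is "a lower average number of drinks per drinking day versus the control group".
- **Scope.** The analysis sentence covers every hypothesis without exception: "These hypotheses will be evaluated using an intention-to-treat comparison of the rates of our primary outcomes at 1-, 2-, and 3-month follow-ups". The measure is fixed in the same sentence: "using incidence rate ratios (IRRs) and 95% CI".
- **Model.** "Given the count nature of much of the data, we will use a Poisson regression covarying for key baseline covariates". No offset, robust variance, scale parameter or overdispersion step is named.
- **Means.** Because the sample is small, "clinically meaningful differences in the pattern of IRRs and means (for alcohol use variables) across groups will be used to evaluate our hypotheses". No model or interval is attached to these means.
- **Second model.** If the results are stable, "generalized estimating equations (GEEs) using binomial distributions and logit-link functions will also be used to explore differences in these outcomes".
- **Linear regression.** It is named only for the exploratory measures: "Descriptive mean comparisons and linear regressions controlling for baseline values will be used to compare whether HIV knowledge and perceived risk" and the other psychosocial scales.

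The protocol does not list this outcome. Its primary outcomes (Measures, efficacy outcomes) are all counts of events or days, and its data analysis plan justifies Poisson by the count nature of the data. The SAP softens that to much of the data, but gives no other model for the hypothesis that is not a count.

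**The concern.** Poisson regression takes the variance of each observation to equal its mean. For a count this is at least a natural starting point, and extra variation can be checked against it. For a per-man average it has no basis. The average is generally not an integer, and its variance depends on how much men differ and on how many drinking days each man contributes. Neither enters the default Poisson standard error.

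A symptom is that the default interval changes with the unit. Recording the same data in half-drinks would multiply the standard error by 1/√2 = 0.707. An interval that uses the observed spread would not change.

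At stake is the precision reported for one of the three alcohol hypotheses. The trial is a pilot meant to prepare a full-scale trial (protocol, Specific Aims). An interval that is too narrow or too wide misinforms that planning, even if nobody relies on a significance test.

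**Working it through.** **Stated figure.** The documents give no SD, target effect or power for this outcome, so there is no planned figure to reproduce.

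**Inputs from the documents.** 40 men are randomised (protocol, Phase 2). The unit is standard drinks, recorded by day on the Timeline Follow-Back (protocol, Measures). The confidence level is 95% (SAP).

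**Assumed inputs.** 1:1 allocation, so n = 20 per arm; no dropout; mean m = 6 drinks per drinking day in both arms; between-man SD of 2, 3 or 4; correlation r = 0.5 between baseline and follow-up averages; gamma-distributed averages in the simulations.

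**Step 1: default Poisson standard error of the log IRR.**

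SE(Poisson) = √(1/(nm) + 1/(nm)) = √(2/(20 × 6)) = 0.129

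No SD appears in the formula.

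**Step 2: standard error implied by the actual spread.**

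- Unadjusted: SE(true) = (SD/m) × √(2/n)
- Adjusted for baseline: replace SD by SD × √(1 − r²) = SD × 0.866

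**Step 3: coverage.** Coverage of the nominal 95% interval ≈ 2Φ(1.96 × SE(Poisson)/SE(true)) − 1.

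| SD | SE(true), unadjusted | Ratio | Coverage | SE(true), adjusted | Ratio | Coverage |
|---|---|---|---|---|---|---|
| 2 | 0.105 | 1.22 | 98.4% | 0.091 | 1.41 | 99.4% |
| 3 | 0.158 | 0.82 | 89.1% | 0.137 | 0.94 | 93.5% |
| 4 | 0.211 | 0.61 | 77.0% | 0.183 | 0.71 | 83.4% |

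The planned model is covariate-adjusted, so the right-hand columns are the relevant ones, provided that the baseline average is among the covariates.

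**Step 4: simulation check.** Unadjusted, 40,000 trials per setting gave 98.5%, 89.3% and 77.3%. A baseline-adjusted simulation gave about 99%, 94% and 83%. Baseline-adjusted linear regression with a t interval covered about 95% at all three SDs.

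**Step 5: where the default interval happens to be right.** The two standard errors agree when the SD equals √m unadjusted (√6 = 2.45), or √m/0.866 = 2.83 after adjustment. Below that the interval is too wide, and above it too narrow.

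**Step 6: a different mean.** With m = 5, unadjusted, the default standard error averaged 0.142 to 0.144 in 1,000 simulated trials per SD, while the SD ran from 1.5 to 4. Coverage fell from 99.9% to 73.6%. In the same trials the Poisson mean model covered 92–95% with a robust variance and 95–96% with a Pearson-scaled variance.

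**The case against.** **The SAP signals an exception.** It calls only much of the data counts and sets means apart for alcohol variables, so it can be read as planning IRRs for counts and means for measures like this one. The reading is possible, but the sentence that assigns IRRs and 95% CIs covers all the hypotheses. The means are given no model, interval or adjustment. The SAP does not rule these out, but it does not supply them either.

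**Poisson is not the only model named.** This is correct: the binomial/logit GEE also covers these outcomes. It is conditional and exploratory, and it suits an average number of drinks no better. What stands is narrower: Poisson is the only model given for the planned IRR and 95% CI.

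**The variance estimator is unstated.** This also stands. A reader might infer that the planned interval necessarily depends on the unit and ignores the spread between men. The documents do not support that: it follows only with default standard errors. A robust or scaled variance largely cures it (step 6).

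**A Poisson model could be right for this quantity.** The Timeline Follow-Back records drinks by day, so total drinks could be modelled with log(drinking days) as offset. The SAP neither names nor excludes this. Ordinary overdispersion would then remain, which is why that route also needs a robust or scaled variance.

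**It is a pilot.** The SAP itself limits conclusions about significance, and no decision rule hangs on this interval. That limits the consequence but does not remove it, since a 95% CI is still promised.

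**Conclusion.** The point holds as a gap in specification. Hypothesis 5 is not a count, and the plan gives its IRR and 95% CI no model except Poisson, with no offset and no robust or scaled variance. If software defaults are used, baseline-adjusted coverage is about 99%, 94% and 83% at SDs of 2, 3 and 4, under the assumptions listed in the working.

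A reader might take the lower unadjusted figures (89% and 77% at SDs of 3 and 4) as the expected size of the error, or conclude that the interval will be too narrow. Neither is supported. The SAP plans covariate adjustment, and the documents give no SD, so both the direction and the size of the error are unknown. At SD 3 the adjusted interval is close to nominal.

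The SAP should be changed. The defect touches one of five hypotheses in a 40-man pilot, and the repair is cheap.

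**What to change.** In the SAP:

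1. Take average drinks per drinking day out of the default Poisson/IRR analysis. At each follow-up, fit a linear regression on arm and the man's baseline average, and report the adjusted mean difference in drinks with a t-based 95% CI. The SAP already names linear regression with baseline adjustment for its exploratory measures. The baseline average exists for every eligible man, because the drinking criterion requires recent heavy drinking. Keep IRRs for the true counts.
2. If an IRR is wanted for this outcome, model total drinks with a log(drinking days) offset and a robust or scaled variance, and say which.
3. State that a man with no drinking days in the window has no defined value. Report the number of such men by arm next to the frequency-of-drinking result, where they count as zero.

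The cost is a few sentences of SAP wording. There are two small downsides. The result is in drinks and not as an IRR. And the comparison is among men who drank in the window, a group formed after randomisation, so it is not a full intention-to-treat comparison. Item 3 lets the reader see how far that matters.
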